In 2013, the InfraScanner 2000™ was introduced, prompting our group to validate it in a consecutive series of 500 head injury patients who obtained a head CT scan at Duke University Hospital (DUH). For all patients with CT-proven bleeds (n=104), irrespective of size, initial NIR scans localized the bleed to the appropriate quadrant with a sensitivity of 86% and specificity of 96% compared to a CT scan. For extra-axial bleeds >3.5ml, sensitivity and specificity were 94% and 96%, respectively. For longitudinal serial rescans with the NIR, sensitivity was 89% (<4 days from injury: sensitivity=99%) and specificity was 96%. The device demonstrated 100% sensitivity for all patients requiring craniectomy or craniotomy.

Since the DUH study, our group initiated a study of 684 TBI patients at Mbarara Regional Referral Hospital (MRRH) in Uganda using the InfraScanner 2000™. For all patients with CT-proven bleeds (n=180), irrespective of size, initial NIR scans localized the bleed to the appropriate quadrant with a sensitivity of 89% and specificity of 38% compared to a CT scan. These findings greatly differ from the DUH data set, prompting our team to conduct a secondary analysis of the MRRH data. We found evidence to suggest that skin tone variance, among other patient characteristics, affects the accuracy of the near-infrared-based device.

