A prospective cohort study is to be conducted at the MRRH Division of Neurosurgery and Mayanja Memorial Hospital (MMH) from May 2024 until May 2025 or until our sample size has been met. Prior to the study, approval from the following institutions and administrations will occur; Duke University IRB approval, Mbarara University of Science and Technology (MUST) IRB approval, Uganda National Council for Science and Technology (UNCST) approval, and administrative approval from both hospitals will be collected.

Methods & Procedures

When applicable (conscious patient and/or family or legally authorized representative (LAR), the study will be introduced to the patient and relevant parties before the research team approaches the patient. While head trauma frequently results in impaired cognition and/or consciousness, and due to the urgency of these circumstances, patients are often not accompanied by kin, whenever appropriate, the purpose of the research and the procedure will be explained in detail using an IRB-approved verbal consent “script”, with all questions answered to the patient’s and/or representative’s satisfaction.

Upon presentation to the casualty unit at MRRH or MMH and/or within 30 minutes prior to or following a CT scan, the study team will approach the patient or the patient’s LAR for permission to scan the patient’s cranium with the InfraScanner 2500™ (Image A). If permission is granted, the study team member will sequentially measure the optical absorption for each of the 8 quadrants of the scalp (frontal, temporal, parietal, and occipital bilaterally) (Image B). The device is engineered such that the light emitter and receiver are spaced 4 cm apart, allowing the light’s intensity to be measured between adjacent light guides (Image C). Parting combs will be used to help access the scalp on patients with hair that prevents the fiberoptic tips from direct contact with the scalp. A laminated swatch displaying Monk Skin Tone Orbs will be used for later analysis of skin tone on the Monk Skin Tone Scale (Image

D).²⁶ This entire procedure, including greeting, scanning the patient, should take <10 minutes. Basic demographics, neuro exam, and InfraScanner 2500™ data will be entered into REDCap (Appendix A).

The collection period for each research subject concludes within 30 days following his or her initial consent, patient or LAR decision to withdraw from further participation, hospital discharge, or patient death, whichever occurs first.

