Frontal Left/Right forehead, above the frontal sinus; Temporal In the Left/Right temporal fossa; Parietal Above the Left/Right ear, midway between the ear and the midline of the skull; Occipital Behind the Left/Right ear, midway between the ear and the occipital protuberance (Image B).

The difference in optical density (ΔOD) in each of the four symmetrical areas is calculated on a pair-wise basis from the following formula:

$$\Delta OD = \log_{10} \left(\frac{I_N}{I_H} \right) = \log_{10}(I_N) - \log_{10}(I_H)$$

where I_N = the intensity of reflected light on the normal side, I_H = the intensity of reflected light on the hematoma side.

In summary: The Infrascanner includes three components: (1) the Scanner, (2) the Disposable Shield, and (3) a Cradle. The Scanner includes a safe NIR diode laser and a silicon detector. The light to and from the laser and detector is optically coupled to the patient's head through the disposable shield optical fibers. The optical fibers are long enough to reach through hair and contact the scalp. The optical fibers are placed 4 cm apart, allowing optimal detection of hematomas. The extended fiber optics eliminates the need to shave off any hair. And because the fiber optic piece is disposable, it prevents cross-contamination. The detected light passes through an optical NIR band-pass filter in order to minimize background light interference. Electronic circuitry is included to control laser power and the detector signal amplifier gain. The detector signal is digitized and analyzed by a single board computer, SBC, in the Scanner. The SBC receives the data from the detector and automatically adjusts the settings of the Scanner to ensure good data quality. The data is further processed by the SBC, and the results are displayed on the screen. A Readout of the scan provides information on the severity of a hematoma and identifies the region of the brain bleeding. A higher optical density in the scanned region indicates a larger hematoma.²⁷

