DHTS - Duke Health Technology Solutions
CT - Computer Tomography
SpO₂ - Oxygen Saturation
SBC - single board computer
LAR - family or legally authorized representative

Image A - Display of Infrascanner device with example of fiber-optic tips making contact with scalp. The scanner includes a safe NIR diode laser and a silicon detector. The light to and from the laser and detector is optically coupled to the patient's head through the disposable shield optical fibers. The optical fibers are long enough to reach through hair and contact the scalp. The optical fibers are placed 4 cm apart

Image B - Head location of Infrascanner Measurements. The Infrascanner is placed successively in the left and right frontal (F), temporal (T), parietal (P), and occipital (O) areas of the head, and the absorbance of light is recorded.

Image C - Depiction of light path from fiber optic source through the scalp intermediate tissue and through the fiber optic detector. From any light source, photons follow a characteristic path through the target tissue back to a detector on the same approximate plane as the source. While the light is severely attenuated due to the scattering and absorption process, it is nonetheless encoded with the spectroscopic signatures of the molecules encountered en route to the detector.

[figure not shown]
Image D - The scale skin tone will be measured against with 1 being the lightest and 10 being the darkest

Image E - The blue line depicts the detected NIR wavelength at 805 nm and the absorption factor is displayed to be sensitive only to blood volume at 805 nm.

Image A

[figure not shown]
Image B

Head location of Infrascanner measurements

- | | |
|------------------|--|
| Frontal | Left/Right forehead, above the frontal sinus |
| Temporal | In the Left/Right temporal fossa |
| Parietal | Above the Left/Right ear, midway between the ear and the midline of the skull |
| Occipital | Behind the Left/Right ear, midway between the ear and the occipital protuberance |

Image C

Target Tissue

Simulated photon diffusion path through target tissue from source to detector.

Image D - MONK SKIN TONE SCALE (1-10)

[figure not shown]
[figure not shown]

Image E

Absorption of light by oxygenated and deoxygenated hemoglobin

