Appendix A

Variable	Type	Description	FITBR Harmonization-Variable Name
finished	T/F	Details if the survey was completed	
ra	Text Entry	Name of Research Assistant completing the survey	
name	Text Entry	Name of patient	
id	Text Entry	Study ID number of patient	SubjectIDNum
age	Numeric	Age of patient	AgeYrs
sex	M/F	Sex of patient	GenderTyp
skin tone	Numeric	Monk Skin Tone Scale (1-10)	
region	Dropdown	Region of Uganda where patient lives	CntryResdnceName
district	Dropdown	District of Uganda where patient lives	
country_other	Text Entry	Country of residence if not Uganda	CntryResdnceName
study_site	Dropdown	Name of site where patient enrolled	SiteName
admit_month	Dropdown	Month of admission	VisitDate
admit_day	Dropdown	Day of the month of admission	VisitDate
admit_year	Dropdown	Year of admission	VisitDate
admit_hours	Numeric	Hour of admission (using 24 hour timing)	ScreenVisitDateTime
admit_mins	Numeric	Minute of the hour of admission (up to 59 mins)	ScreenVisitDateTime
temp	Numeric	Temperature on admission	
admit_eye	Numeric	Admit GCS eye opening	GCSEyeRespnsScale
admit_verbal	Numeric	Admit GCS verbal	GCSVerbalRspnsScale
admit_motor	Numeric	Admit GCS motor	GCSMotorRespnsScale
admit_gcs	Numeric	Admit GCS total	GCSTotalScore
neuro_month	Dropdown	Month of neuro exam	
neuro_day	Dropdown	Day of the month of neuro exam	
neuro_year	Dropdown	Year of neuro exam	
neuro_hours	Numeric	Hour of neuro exam (using 24 hour timing)	
neuro_mins	Numeric	Minute of the hour of neuro exam (up to 59 mins)	

infra_eye	Numeric	Infrascanner GCS eye opening	GCSEyeRespnsScale
infra_verbal	Numeric	Infrascanner GCS verbal	GCSVerbalRspnsScale
infra_motor	Numeric	Infrascanner GCS motor	GCSMotorRespnsScale
infra_gcs	Numeric	Infrascanner GCS total	GCSTotalScore
injury_month	Dropdown	Month of TBI	InjDateTime
injury_day	Dropdown	Day of the month of TBI	InjDateTime
injury_year	Dropdown	Year of TBI	InjDateTime
injury_hours	Numeric	Hour of neuro exam (using 24 hour timing)	
injury_mins	Numeric	Minute of the hour of neuro exam (up to 59 mins)	
hair_scalp_access	Y/N	hair status occludes access to scalp	
hair_scalp_access_reason	Text Entry	Text entry if hair status did not allow for access to scalp	
trauma	Dropdown	Cause of trauma	
trauma_other	Text Entry	Text entry if cause of trauma was not listed	
polytrauma	Y/N	Polytrauma present	
rta	Dropdown	Cause of road traffic accident	
rta_other	Text Entry	Text entry if cause of RTA was not listed	
scalp	Y/N	Scalp or face hematoma present	

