scalp_text	Text Entry	Location of scalp or facial hematoma	
facial_bleed	Multi-select	Bleeding from eyes, ears, or nose present	
skull	Y/N	Skull fracture present	
skull_bones	Multi-select	Location of skull fracture	
scalp_injury	Y/N	Open scalp injury present	
surgery_planned	Y/N	A surgery was planned	
surgery	Y/N	A surgery was completed	
surgery_month	Dropdown	Month of surgery	
surgery_day	Dropdown	Day of the month of surgery	
surgery_year	Dropdown	Year of surgery	
surgery_type	Multi-select	Type of surgery performed	
surgery_type_other	Text Entry	Text entry if surgery type not listed	

ct	Y/N	A CT was completed	
ct_month	Dropdown	Month of CT	
ct_day	Dropdown	Day of the month of CT	
ct_year	Dropdown	Year of CT	
ct_hours	Numeric	Hour of CT (using 24 hour timing)	
ct_mins	Numeric	Minute of the hour of CT (up to 59 mins)	
ct_no	Multi-select	Details why a CT was not completed	
ct_no_other	Text Entry	Text entry for no CT if not listed	
infra_1_month	Dropdown	Month of first infrascanner	
infra_1_day	Dropdown	Day of the month of first infrascanner	
infra_1_year	Dropdown	Year of first infrascanner	
infra_1_hours	Numeric	Hour of first infrascanner (using 24 hour timing)	
infra_1_mins	Numeric	Minute of the hour of first infrascanner (up to 59 mins)	
infra_1_positive	Y/N	First infrascanner with a positive result	
infra_1_frontal	Numeric	First infrascanner numeric result in frontal area	
infra_1_parietal	Numeric	First infrascanner numeric result in parietal area	
infra_1_temporal	Numeric	First infrascanner numeric result in temporal area	
infra_1_occipital	Numeric	First infrascanner numeric result in occipital area	
outcome_month	Dropdown	Month of outcome	
outcome_day	Dropdown	Day of the month of outcome	
outcome_year	Dropdown	Year of outcome	
outcome	Dropdown	Outcome of patient	
disc_eye	Numeric	Discharge GCS eye opening	GCSEyeRespnsScale
disc_verbal	Numeric	Discharge GCS verbal	GCSVerbalRespnsScale
disc_motor	Numeric	Discharge GCS motor	GCSMotorRespnsScale
disc_gcs	Numeric	Discharge GCS total	GCSTotalScore

gose	Numeric	GOSE on discharge	GlasgowOutcomeScaleExtScore
ct_pos	Y/N	CT with positive findings	
ct_fl	Dropdown	Type of bleed on CT frontal left	
ct_fr	Dropdown	Type of bleed on CT frontal right	
ct_pl	Dropdown	Type of bleed on CT parietal left	
ct_pr	Dropdown	Type of bleed on CT parietal right	
ct_tl	Dropdown	Type of bleed on CT temporal left	
ct_tr	Dropdown	Type of bleed on CT temporal right	
ct_ol	Dropdown	Type of bleed on CT occipital left	

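### Skin tone is a visual 1–10 match that the protocol neither places before the device reading nor masks from it, so the exploratory skin-tone association is open to rating bias

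*Combined protocol and SAP*

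**What the plan says.** **Measurement.** Section 5 (Methods & Procedures) describes the scan first: "the study team member will sequentially measure the optical absorption for each of the 8 quadrants of the scalp". Parting combs come next, then the swatch: "A laminated swatch displaying Monk Skin Tone Orbs will be used for later analysis of skin tone on the Monk Skin Tone Scale". Appendix A stores the score as one numeric field, "Monk Skin Tone Scale (1-10)", and the Image D legend gives its direction, "with 1 being the lightest and 10 being the darkest". No rater, body site, moment of rating or repeat reading is specified. Appendix A has hour and minute fields for the CT and the first InfraScanner reading, but none for the skin-tone score.

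**Visibility of the result.** Section 12 says of the scanner that "the results are displayed on the screen". The Appendix A form has one completer field, "Name of Research Assistant completing the survey", and also holds the device outcome, "First infrascanner with a positive result".

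**Masking.** Section 13 masks the treating physicians to device data. Section 15(b) masks patients and care providers. Neither mentions the person who scores skin tone.

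**Use.** Section 15 enters skin color in a logistic regression of the device result, conditioned on CT, and lists skin tone among the factors in exploratory objective 1. Aim 2 concerns accuracy in darker-skinned populations. The Background reports, for the earlier 2000 model in Uganda, "We found evidence to suggest that skin tone variance, among other patient characteristics, affects the accuracy". It offers dark skin as a possible source of false positives.

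**The concern.** A visual match to a ten-point swatch leaves room for judgement between neighbouring steps. If the person choosing the step already knows whether the device read positive, the error in the score can depend on the outcome it is later regressed against. Such error can create an association that does not exist or hide one that does.

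The analysis could not repair this. The planned data contain no rating time, named rater, second reading or objective measure of pigmentation, so nobody could show afterwards that the ratings were independent of the results. Skin tone is also the reason the protocol gives for studying the new model: specificity was 96% at the US site and 38% in Uganda with the 2000 model. An unreliable skin-tone association would weaken the answer to that question.

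**Working it through.** The plan gives no figure for this point, so there is none to reproduce. The check has two parts: what the text permits, and how much a given drift would matter.

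**1. What the text permits**

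- A study team member scans (section 5), and the result appears on the scanner (section 12).
- One form carries both the skin-tone score and the device result (Appendix A).
- Masking applies to patients, care providers and treating physicians only (sections 13 and 15(b)).
- No sentence puts the rating before the reading.

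A rating made after the result is seen would therefore comply with the protocol, and so would one made before. The text does not choose between them.

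**2. Size, under stated assumptions**

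Inputs from section 15(c): 171 patients with CT and 46% prevalence, so CT-negative patients = 171 × (1 − 0.46) = 92.3, taken as 92. Specificities of 38% and 96% are those the Background reports for Uganda and the US site. The values 70% and 90% are intermediate assumptions.

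Assumed: Monk tone = a normal value with mean 8 and SD 1, rounded and limited to 1–10; no true link between tone and device result; a stated share of device-positives rated one step darker. The test is a two-sided Wald test at 0.05 from a logistic regression of device result on tone.

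Quick check of the odds ratio: log OR per step ≈ mean shift ÷ variance. Rounding adds 1/12 to the variance, giving 1.083. With 20% drift, 0.20/1.083 = 0.185, and exp(0.185) = 1.20.

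Simulated results:

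| Device-positives rated one step darker | OR per step | Type I error, specificity 38% or 70% | 90% | 96% |
|---|---|---|---|---|
| 0% | 1.0 | about 5% | about 4% | about 3% |
| 10% | 1.07–1.10 | 6–7% | 5–6% | 3–4% |
| 20% | about 1.2 | about 12% | about 8% | 4–5% |
| 30% | about 1.3 | 20–22% | 11–12% | about 6% |

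The odds ratio hardly depends on specificity. The error rate does, because it depends on how many false positives there are: 92 × 0.62 = 57 at 38%, 92 × 0.30 = 28 at 70%, 92 × 0.10 = 9 at 90% and 92 × 0.04 = 4 at 96%. At 96%, the few simulated trials that could not be fitted were left out.

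**Sensitivity to the tone spread.** A second model used mean 7, added random reading error with SD 0.5, and put drift at 25%. With a tone SD of 1.0, the error rate was about 15% at a false-positive share of 62% or 30%, and 9% at 10%. With a tone SD of 1.5, these became about 10% and 6%, and the odds ratio fell from 1.2 to 1.1.

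**Opposite direction.** Rating device-positives one step lighter at specificity 38–70% gives odds ratios of about 0.83 at 20% drift and 0.76–0.77 at 30%. That could mask a true effect of similar size.

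**The case against.** The strongest reply is that no passage says the rater knows the result. Several points support it, and they stand:

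- Sentence order in section 5 is not a procedural sequence. The parting combs also follow the scan sentence, yet must be used before or during it.
- Section 12 is a generic device description adapted from the manufacturer's white paper. The completer field in Appendix A names who fills in the form, not who holds the swatch.
- Appendix A lists skin tone directly after age and sex, well ahead of the device fields. That points towards a baseline rating.
- The swatch sentence's reference to later analysis most naturally means statistical analysis of a bedside score, not a rating made later.

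A reader might also infer that the team expects darker skin to cause false positives with this device. The documents do not support that. The hypothesis is hedged and concerns the 2000 model, while the 2500 is described as adjusting for skin tone. An expectation of no association is equally possible, so the direction of any bias is open.

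Nor does the whole of Aim 2 rest on the score, since it can be read partly as overall accuracy in this cohort. Exploratory objective 1 also covers hematoma type, location and age. Finally, the drift rates are not drawn from the documents, and if specificity matches the US site the error rate barely moves.

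These points limit the claim but leave the gap: the protocol does not prevent the result from influencing the score, and no planned data could show that it had not.

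**Conclusion.** The concern holds as a missing safeguard on an exploratory analysis. The rater can, but need not, have seen the device result, and any bias could run either way. The documents do not show that it will occur.

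What is exposed is the skin-tone association in exploratory objective 1 and the logistic regression, and the part of Aim 2 that draws on it. The primary estimates of sensitivity and specificity do not use the score.

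If 20% of device-positives drifted by one step, the false odds ratio would be about 1.2 per step. The false-association rate would be about 12% if specificity stays between 38% and 70%, and about 8% at 90%. At 96% the test is not materially inflated, although the odds ratio is still shifted. These figures rest on assumed values for drift, tone spread and absence of a true effect. They show that the mechanism could matter at this sample size, not that it does. The change is worth making because it removes this route of bias at almost no cost.

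**What to change.** In section 5 (Methods & Procedures), state that the study team member matches Monk tone against the swatch at a fixed site, for example the forehead next to the frontal probe site. The score is recorded before the first InfraScanner reading and not changed afterwards.

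In REDCap, make the skin-tone field required before the infra_1 fields open. A REDCap rule controls only the order of entry, so where entry is not at the bedside, the score should be written on the source sheet before scanning begins.

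The cost is the reordering of an existing step and one database rule, with no extra staff, procedure or visit time. This removes the influence of the device result on the rating. It does not reduce ordinary random rating error.

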Assessment of Accuracy, Precision, and Feasibility of a Handheld Near-Infrared
Light Device (InfraScanner 2500™) in Detecting Traumatic Intracranial
Hemorrhage in Uganda

Document Date: 05/29/2024

NCT06491173

1. Title

Assessment of Accuracy, Precision, and Feasibility of a Handheld Near-Infrared Light Device (InfraScanner 2500™) in Detecting Traumatic Intracranial Hemorrhage in Uganda

2. Study Team

Duke

Principal Investigator: [name], *MD, PhD*
Co-Principal Investigator: [name], *MBBS, MSGH*
Co-Principal Investigator: [name], *MD, PhD, MACM*
Study Coordinator: [name], *BS*

Mbarara

Principal Investigator: [name], *MChB, MMED, FCS*
Study Coordinator: [name], *RN, BNS, MNS*

- Purpose of the Study:** The purpose of this study is to determine the sensitivity, specificity, and positive and negative predictive values of the portable near-infrared-based device (portable NIR-based device), the InfraScanner 2500™, to detect intracranial hemorrhage (ICH) secondary to trauma patients presenting to Mbarara Regional Referral Hospital (MRRH) and Mayanja Memorial Hospital (MMH) who have sustained or who are suspected of having sustained head trauma.
- Background and Significance:** In 2018, an estimated 69 million individuals sustained traumatic brain injury (TBI), with the majority of cases originating in LMICs.^{1,2} With approximately 90% of all injury-related vehicular deaths occurring in LMICs, this already enormous chasm in mortality is expected to only grow wider as obtainability of personal motor vehicles burgeons at rates far exceeding LMIC faculties to build legislative, municipal, and medical infrastructure capable of subsiding growing incidence of TBI.³ Sub-Saharan Africa's unprecedented scarcity of medical resources is especially prominent in neurological care. As of July 2023, there are 0.15 neurosurgeons per 100,000 Africans.⁴ This can be contrasted with Europe where, per 100,000 citizens, there exist 17.1 neurological beds, 4.84 neurologists, and 2.43 neurosurgeons – a respective 57, 161, and 16-fold resource disparity between these two continents. Even when compared to global averages, to which Africa and myriad other LMICs contribute, per capita, the world's population benefits from greater than 12 times more neurological beds, 30 times more neurologists, and 56 times more neurosurgeons per capita than the average African.⁵

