6. **Eligibility:** Any patient aged 12 and up who presents to Mbarara Regional Referral Hospital (MRRH) or Mayanja Memorial Hospital (MMH) with suspected head trauma, who is able to or who has a LAR who is able to consent in English, Runyankole, or Luganda will be considered for this study. After being made aware of the study by a physician directly caring for the patient and agreeing to hear more about the study, the prospective participant and/or the participant's LAR will be approached.
7. **Exclusion:** Patients for which wounds to their head are too large to properly use the InfraScanner 2500™ will be excluded from this study. Patients will also be excluded if hair cannot be appropriately parted to allow for the fiberoptic tips of the device to make direct contact with the scalp. Patients for whom it is not possible to obtain an Infrascan within 30 minutes of their CT imaging will also be excluded from the study.
8. **Subject Recruitment and Compensation:** Potential research participants will be approached by the research team only if given permission by the physician in charge of the patient's care after he or she has informed the patient and/or the patient's LAR of the research and received a verbal agreement from the patient and/or LAR to hear more about the research study. Each participant will be compensated UGX 15,000 (\$4) for participation in this study. The study personnel will be trained in the consent process and will make it abundantly clear that agreement or refusal to participate in the study will not influence the patient's care in any way.

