With 84 patients with positive findings of hematoma (i.e. CT-proven ICH), sensitivity can be estimated to be within at most +/- 0.099 with 95% confidence.³¹ Assuming 46% of patients have true hematomas detected,²⁸ 171 patients who obtain CT scans must be accrued. Accounting for this, and allowing for a 5% dropout rate the required sample size for this trial is 180 total subjects.^{29,30} We estimate that 50% of TBI patients will obtain CT scans, thus approximately 360 TBI patients will present to MRRH and/or MMH to reach our desired sample size.

d) Recruitment and Retention

It is anticipated that of all participants >12 years of age that present with suspected TBI, at least 40 patients per month will be accrued . Study enrollment should thus be completed within approximately 10 months. The collection period for each research subject concludes within 30 days following their initial consent, patient or LAR decision to withdraw from further participation, hospital discharge, or patient death; whichever occurs first.

16. Data and Safety Monitoring: Patients will be under continuous supervision during the entirety of each data collection period. Outside the ~10-minute window of the data collection period, the patient is not subjected to any research intervention or influenced by the research in any way. As part of their treatment, patients will be under hospital care for the diagnoses for which they were admitted, and the research team will be in continual contact with the team regarding their clinical status and enrollment in the study.

The PI will be responsible for securing and monitoring the data, including a quarterly review of data storage procedures.

17. Privacy, Data Storage, and Confidentiality: Patients will be numbered as experimental subjects. Data will be stored in a secure database. For analysis, data will be fully de-identified. Experimenters' notes will be stored in a locked cabinet in the PI's office in the Department of Neurosurgery and in digital form on the DHTS-maintained server.

18. Limitation of study

This study will not include patients whose injuries impede the use of the device onto the scalp which may exclude TBI cases of greater severity, potentially biasing results towards less severe TBI cases.

ABBREVIATIONS LIST

MRRH - Mbarara Regional Referral Hospital

MMH - Mayanja Memorial Hospital
TBI - Traumatic Brain Injury
LMIC - Low- and Middle-Income Country
SSA- Sub-Saharan Africa
DUH - Duke University Hospital

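### Patients who cannot be scanned because of hair or wounds are excluded, and no feasibility outcome is defined, so accuracy is conditional on a completed scan and the rate of unobtainable scans may go unreported

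*Combined protocol and SAP*

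**What the plan says.** The title begins "Assessment of Accuracy, Precision, and Feasibility". The purpose, the two aims and the objectives in section 15 all concern test performance. None of them gives feasibility an outcome, a denominator, a success criterion or an analysis.

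Section 7 has three exclusions:

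- Wounds: "Patients for which wounds to their head are too large to properly use the InfraScanner 2500™ will be excluded from this study".
- Hair: "Patients will also be excluded if hair cannot be appropriately parted" for the tips to touch the scalp.
- Timing: no InfraScan could be obtained within 30 minutes of the CT.

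Section 15(b) defines sensitivity and specificity for a device result that is either positive or negative. It gives no rule for a scan that fails or is incomplete.

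Appendix A has a yes/no item described as "hair status occludes access to scalp", with a free-text reason. It also records whether an open scalp injury is present. The device result is yes/no only. No item records that a wound or a device error prevented the scan, although there is an item for why a CT was not done.

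Section 18 concedes that leaving out patients whose injuries impede the device is "potentially biasing results towards less severe TBI cases". It does not mention hair and offers no analysis.

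**The concern.** Hair that blocks the fibres and wounds that prevent contact are ways in which this device can fail in use. If these patients leave the study uncounted, the report will give accuracy among patients who could be scanned and nothing on how many could not.

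Aim 1 asks whether the device is good enough to serve as a triage tool, and section 6 opens the study to any suspected head trauma from age 12. A patient who cannot be scanned gets no answer from the device. Without the failure proportion, a reader cannot move from accuracy in scanned patients to performance in the patients who present. The feasibility named in the title also stays unanswered.

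Some of these failures may surface only after consent. Section 5 places the parting combs at the scanning step, once permission has been granted, so a hair exclusion can depend on how the attempt went.

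**Working it through.** **The plan's own figures.** The plan states no failure rate. The only related figures are in section 15(c): 171 patients with CT and 5% dropout give 171 / 0.95 = 180, which reproduces. (The preceding step does not: 84 / 0.46 = 182.6, against the stated 171. That is a separate matter and nothing below depends on it.) Section 15(c) plans a half-width of at most 0.099 for sensitivity.

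**Inputs for the illustration.**

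- Sensitivity Se = 0.89 and specificity Sp = 0.38, from the earlier Ugandan study of the previous model (Background and Significance).
- Failure share f: not in the documents. I assume 2% to 20%, equal in patients with and without a bleed.

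**Formulas.**

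- Failures counted as negative: sensitivity = Se(1 − f); specificity = Sp(1 − f) + f.
- Failures counted as positive: sensitivity = Se(1 − f) + f; specificity = Sp(1 − f).

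| f | Sensitivity, failures negative | Sensitivity, failures positive | Specificity, failures negative | Specificity, failures positive |
|---|---|---|---|---|
| 2% | 87.22% | 89.22% | 39.24% | 37.24% |
| 5% | 84.55% | 89.55% | 41.10% | 36.10% |
| 10% | 80.10% | 90.10% | 44.20% | 34.20% |
| 20% | 71.20% | 91.20% | 50.40% | 30.40% |

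When failures count as negative, the loss in sensitivity is 0.89f. It exceeds the planned half-width of 0.099 once f is above 0.099 / 0.89 = 0.111, about 11%.

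**How well the failure share could be estimated.** Exact 95% intervals with 180 patients as denominator:

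- 9/180 (5%): 2.3% to 9.3%
- 18/180 (10%): 6.0% to 15.3%
- 36/180 (20%): 14.4% to 26.6%

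**Effect on the sample.** Keeping 171 scanned patients needs 171 / (1 − f) patients, rounded up: 175 at 2%, 180 at 5%, 190 at 10% and 214 at 20%. If unscannable patients were counted inside the 180, a 20% share would leave 180 × 0.80 = 144 evaluable.

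**The case against.** The strongest reply is that accuracy conditional on a valid scan is a legitimate quantity, that the stated aims concern accuracy only, and that section 18 discloses the injury selection. Feasibility as a study goal appears only in the title, so rewording the title would also remove the mismatch. Failures may be few as well: section 12 says the fibres reach through hair, and combs are provided. All of this stands. It limits the size of the point, but it does not supply the missing count.

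A reader might also infer stronger claims that the documents do not support:

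- *That the trial cannot report feasibility at all.* Hair failures could be counted if the Appendix A item were completed for excluded patients. The plan does not say whether it is.
- *That every device failure is removed.* Section 7 names hair, wounds and timing. On device error and incomplete scans the plan is silent.
- *That accuracy is biased upward.* This holds for both measures only if each failure is scored as wrong, that is, negative in a patient with a bleed and positive in one without. No single scoring rule does that. Under either uniform rule one measure falls and the other rises.
- *That the exclusion spoils the regression on hair factors.* That model needs a device result, so a patient without one cannot enter it under any design.

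**Conclusion.** The point holds as a gap in what the trial will be able to report. The planned accuracy estimates are valid for patients with a completed scan, but the plan neither labels them so nor provides for reporting the share without one.

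The size is unknown because the documents give no failure share. At an assumed 2% the change in sensitivity is under 2 points. At 20% sensitivity runs from 71% to 91%, and specificity from 30% to 50%, depending on scoring. These figures rest on an assumed range, on equal failure in patients with and without bleeds, and on accuracy values from the previous model, whose algorithm has since changed. Section 18 suggests that wound exclusions may fall on more severe cases. If failures are more common in patients with bleeds, the sensitivity column should be read at that higher share.

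The change is worth making because it is cheap and settles which of these cases applies.

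**What to change.** **Section 7.** Record every approached eligible patient with CT in whom no valid reading is obtained as 'scan not obtainable', with a coded reason: hair, wound or device error. Include patients seen to be unscannable before any attempt, since a denominator of attempted scans alone would miss them. Record missed 30-minute windows as a separate, logistic category.

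**Section 15.** Report the proportion not scannable, with an exact 95% CI, as the feasibility outcome. Label the primary accuracy analysis as conditional on a valid scan. Add a sensitivity analysis that counts failures once as negative and once as positive. These are scoring conventions for analysis, not rules for care.

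**Sample size.** Count these patients in addition to the evaluable-scan target, so that precision is not eroded.

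**Appendix A.** Add the coded reason field, and state that it and the hair-access item are completed for patients who are not scanned.

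**Cost.** One field, one table and possibly a less favourable secondary figure. No extra scans are needed: reaching the same number of evaluable scans already means passing over unscannable patients, and the change is that they are recorded. Any who are enrolled would receive the UGX 15,000 in section 8. At a 20% share that is 214 − 171 = 43 patients, or UGX 645,000. Patients who have not consented could contribute a count and reason only, subject to ethics approval; the two-way analysis needs their CT result and so needs consent.
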